Key secondary safety endpoint

- Occurrence of bleeding, as defined by BARC type ≥ 3B, within 30 days and one year after study enrollment expressed as a proportion of patients with any of these events.

Other secondary endpoints

The following endpoints will be expressed as the proportion of patients with events:

- Death, myocardial infarction, urgent revascularization of the infarct-related artery, stroke, or major bleeding as defined by the BARC (Bleeding Academic Research Consortium) criteria* on day 30 and one year after study enrollment expressed as a proportion of patients with any of these events.

**BARC type $\geq 3B$*

- Cardiovascular death, myocardial infarction, urgent revascularization, and heart failure on day 30 and one year after study enrollment.
- Individual components of the primary clinical endpoint on day 30 and one year after study enrollment.
- Heart failure* on day 30 and one year after study enrollment.

**New heart failure or hospitalization for heart failure*

- Cardiovascular death on day 30 and one year after study enrolment.
- Occurrence of bleeding as defined by BARC type $\geq 3B$ within 30 days after study enrolment.
- Occurrence of stent thrombosis within 30 days after study enrolment.
- Delayed* aortocoronary bypass surgery due to a risk of bleeding within 30 days after study enrolment.

**Assessed by the heart team, indicating aortocoronary bypass surgery.*

- Effective* P2Y₁₂ platelet receptor inhibition defined by Platelet Reactivity Index (PRI) value 1 hour after PCI.

**Platelet Reactivity Index (PRI) less than 50% as measured by the vasodilator-stimulated phosphoprotein (VASP) phosphorylation flow cytometric assay*

The following endpoints will be displayed as the median and interquartile range (IQR):

- Duration of vasoactive pharmacotherapy and/or mechanical circulatory support in days.
- Duration of hospitalization* in days.

**Intensive care unit stay and total hospital stay*

- Maximum values of high-sensitive cardiac troponin in μg per liter.

Other pursued goals

- Cost-effectiveness is expressed as a comparison of the costs of treatment (including days of hospitalization, ICU stays, medical procedures, and pharmacotherapy) and its effect on the occurrence of endpoints. This is measured as the cost per avoided event up to day 30 and up to 1 year after randomization.

Sample size calculation

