Standard descriptive statistics will be employed in the analysis to summarize both categorical and continuous variables. For categorical variables, data will be presented as absolute frequencies (i.e., counts) and relative frequencies (i.e., percentages), clearly representing each category's distribution across the study groups. For continuous variables (including pharma-economic data), the data will be reported either as the median supplemented with the interquartile range (IQR) or the 5th to 95th percentiles range, which captures the central tendency and spread in a non-parametric manner or as the mean supplemented with the standard deviation, which provides a measure of central tendency and variability under the assumption of normal distribution. The choice between median and mean reporting will depend on the distributional properties of the continuous variables. Data visualization will use standard box and whisker plots for continuous variables and bar plots for categorical variables. Relative risks and 95% confidence intervals will be used to describe and visualize the results of endpoint analysis.

The chi-square test will be employed for categorical variables, including the primary and secondary study endpoints and all other relevant categorical data, to assess the statistical significance of observed differences between groups. This test will evaluate whether the observed frequencies in different categories deviate from what would be expected under the null hypothesis. The Mann-Whitney U test will be applied for continuous variables, as it is a robust non-parametric alternative to the t-test, particularly useful when the assumption of normality is not met. This test will determine whether there are statistically significant differences in the distribution of continuous variables between the study arms. The non-inferiority scenario will be assessed using a one-sided Z-test with a non-inferiority margin of 1%.

To ensure comparability among centers, the data for analyzing maximum values of high-sensitivity cardiac troponin will be presented as the ratio of the maximum value within seven days to the reference value for myocardial infarction at a specific center.

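### The SAP's only rule for cost data (median or mean by distribution, Mann-Whitney U) does not fit its own measure, cost per avoided event, which needs arithmetic mean costs

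*SAP*

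**What the plan says.** Under "Other pursued goals", after the secondary endpoints, the SAP describes cost-effectiveness as a "comparison of the costs of treatment (including days of hospitalization, ICU stays, medical procedures, and pharmacotherapy" and so on, set against the effect on endpoints. It then fixes the measure: "This is measured as the cost per avoided event up to day 30 and up to 1 year after randomization".

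The summary rule is in the second section headed Statistical analysis, which follows Data Sharing. It opens with "For continuous variables (including pharma-economic data" and offers two forms: the median with IQR or 5th to 95th percentiles, or the mean with SD. The mean is linked to a normality assumption. The choice is settled by "The choice between median and mean reporting will depend on the distributional properties of the continuous variables". For comparing arms, "The Mann-Whitney U test will be applied for continuous variables"; the SAP describes that test as detecting differences in distribution.

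The section on missing values and outliers adds that outliers found by visual inspection are dropped from computations. Costs are not exempted. The SAP gives no formula for the ratio and no separate method for costs.

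**The concern.** A cost per avoided event answers a budget question: how much more is spent, in total, for each event prevented. Only the arithmetic mean multiplies up to a total, so the numerator must be a difference in means whatever the shape of the distribution. The SAP makes the choice of summary depend on shape, and it names cost data as covered.

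Costs built from hospital days, ICU stays and procedures are very likely to be skewed. The SAP itself plans median and IQR for length of stay and duration of circulatory support, which drive cost. An analyst who follows the text would therefore tabulate median costs and a Mann-Whitney p-value. Neither describes the mean cost difference. A reader could then see a ratio, a median cost per arm and a p-value that refer to three different quantities.

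**Working it through.** **No plan figure to reproduce.** The SAP states no cost, cost SD or cost-effectiveness result. The only SAP input used is the superiority planning pair, 50% versus 38%. The usual two-proportion formula (two-sided 0.05, power 0.80) with this pair gives 536 in total, as stated. All cost levels and spreads below are assumptions.

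**Target quantity.** Cost per avoided event = (mean cost, cangrelor − mean cost, ticagrelor) / (event proportion, ticagrelor − event proportion, cangrelor). With the planning pair the denominator is 0.50 − 0.38 = 0.12.

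**Step 1: mean against median within one arm.** For log-normal costs, mean/median = √(1 + CV²). This is 1.12 at CV 0.5, 1.41 at CV 1, 1.80 at CV 1.5 and 2.24 at CV 2. These ratios concern the level within an arm, not the difference between arms, so they do not give the error in the ratio.

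**Step 2: difference between arms.** Assume costs are a mixture of patients who die and patients who survive, each log-normal, with 50% versus 38% deaths. (The SAP's pair refers to the composite endpoint; using it for deaths is a simplification.)

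- Mean of a component with median m and log-SD s: m·exp(s²/2). The mean cost difference is therefore 0.12 × (mean of survivors − mean of deaths).
- Median x of an arm with death proportion p solves p·Φ(ln(x/m_d)/s_d) + (1 − p)·Φ(ln(x/m_s)/s_s) = 0.5.

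For the first row below, the component means are 8·exp(0.18) = 9.58 and 20·exp(0.32) = 27.54, so the mean difference is 0.12 × 17.96 = 2.16. The arm medians are 11.85 and 13.49, a difference of 1.64. Per avoided event this is 2.16/0.12, about 18.0, against 1.64/0.12, about 13.7.

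| Deaths: median, log-SD | Survivors: median, log-SD | Mean difference | Median difference | Median-based relative to mean-based |
|---|---|---|---|---|
| 8, 0.6 | 20, 0.8 | 2.16 | 1.64 | 24% below |
| 8, 0.6 | 20, 1.0 | 2.81 | 1.49 | 47% below |
| 8, 0.6 | 20, 0.6 | 1.72 | 1.78 | 3% above |
| 4, 0.6 | 20, 0.8 | 2.73 | 2.89 | 6% above |
| 5, 0.6 | 25, 0.6 | 2.87 | 4.29 | 49% above |

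These are examples, not bounds. Modest changes in the assumptions reverse the direction.

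**Step 3: unequal skewness.** Take medians of 10,000 (control, CV 1.5) and 11,000 (cangrelor, CV 1.0). The medians give +1,000, or 1,000/0.12 = 8,333 per avoided event. The means are 10,000·√3.25 = 18,028 and 11,000·√2 = 15,556, a saving of about 2,471. The sign changes.

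**Step 4: outlier removal.** The SAP gives no numerical cut. If visual inspection acted like a boxplot limit (above Q3 + 1.5 IQR), simulated log-normal costs lose 6.5% of patients and about 20% of the mean at CV 1, and 8.4% of patients and about 33% of the mean at CV 1.5. Even an analysis of means would then leave out real costs.

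**The case against.** The strongest reply is that the rule on medians and means governs descriptive reporting, and that cost per avoided event is defined elsewhere. A reader might infer that the SAP will put median costs into the ratio and so report a wrong result. No sentence says so, the rule also permits means, and medians are legitimate as description. This part of the objection stands: what can be shown is an unsuitable stated rule and an unspecified input, not a stated wrong calculation.

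A reader might also infer a definite bias, such as a ratio about a quarter too low. One set of assumptions gives that; others give an error in the opposite direction. Nor is Mann-Whitney reserved for skewed variables: the SAP assigns it to continuous variables generally and does not claim that it tests mean cost.

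Finally, the ratio formula and its interval may sit in the protocol or a separate economic plan, neither of which is at hand. Their absence from the SAP is therefore not counted as an error in itself. This does not remove the point, because the SAP is not silent on costs: it expressly places them under the general rule. A document elsewhere that called for mean costs would conflict with that text until it was amended.

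**Conclusion.** The point holds as a mismatch within the SAP. The measure requires a difference in arithmetic means. The only rule stated for cost data leads to medians when costs are skewed, and to a test that does not address mean cost. The conclusion that means are needed follows from the definition of the measure and rests on no assumption about costs. That the rule would lead to medians rests on costs being skewed, which is likely but not documented with data.

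Neither the size nor the direction of any error can be given from the SAP; the span of about 47% below to about 49% above comes from assumed mixtures only. Importance is minor: no primary, secondary or safety conclusion depends on it.

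**What to change.** In the second Statistical analysis section, remove pharma-economic data from the median/mean rule and from the Mann-Whitney rule. Add a short paragraph stating that:

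- cost per avoided event, to day 30 and to 1 year, uses the arithmetic mean cost per arm regardless of skewness;
- the mean cost difference and the ratio are given with bootstrap 95% intervals, resampling patients so that each patient's cost and event status stay together;
- median costs may be shown as description only;
- costs are exempt from the visual outlier removal, apart from correction of data errors.

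If an economic plan already says this, a cross-reference is enough once the conflicting wording is removed. The cost is a few sentences and a standard bootstrap, with no new data. The intervals will be wide, and the interval for the ratio may be unstable if the event difference is close to zero.

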- Statistical significance level 0.05
- Endpoint occurrence in the control group 70%
- Endpoint difference 20%.

Based on the event rates of 70% in the control group and 90% in the cangrelor group, 124 patients are needed to test the null hypothesis of no difference between groups. The required sample size fits the reachable number of VASP measurements, which is approximately 150.

Power analysis for the primary clinical endpoint (death from any cause, myocardial infarction, or stroke within 30 days)

Power analysis was performed for two scenarios: (i) the experimental group's non-inferiority and (ii) the experimental group's superiority to the control group. The sample size is computed for the patients who will receive the initial dose of the study drug. The analysis was performed in PASS 13 software (Hintze, J. (2014)). PASS 13. NCSS, LLC. Kaysville, Utah, USA. www.ncss.com).

Power analysis for non-inferiority scenario

The analysis was performed with the following settings:

- Test power 0.8
- Statistical significance level 0.05
- Endpoint occurrence in the control group based on relevant studies 50%
- Endpoint difference 10 % with a noninferiority margin of 1%.

Based on the event rates of 50% in the control group vs. 40% in the Cangrelor group and the noninferiority margin of 1%, 506 patients are needed to test the noninferiority hypothesis.

Power analysis for the superiority scenario

The analysis was performed with the following settings:

- Test power 0.8
- Statistical significance level 0.05
- Endpoint occurrence in the control group based on relevant studies 50%
- Endpoint difference 12%.

Based on the event rates of 50% in the control group vs. 38% in the Cangrelor group, a total of 536 patients is needed to test the null hypothesis of no difference between groups. Allowing for a 3% drop-out rate, 550 patients should be enrolled. The drop-out rate is based on settings of multiple clinical studies, and a higher drop-out rate is not expected in our study.

Schedule of study visits

The study started in August 2018 and reached N=304 enrolled patients in August 2021, as planned in the original version of the protocol. The end of the collection of the extended sample size, according to AMENDMENT 2 of the study protocol, is planned for January 2024. For each patient, the following order of case report forms is planned (Table 1):

- Randomization,

- Visit 1 - admission to the hospital on the first day,
- Visit 2 – Follow-up on day 7,

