A p-value of 0.05 will be adopted as the threshold for determining statistical significance across all analyses. All statistical analyses will be conducted in strict accordance with the regulatory guidelines outlined in the E9 Statistical Principles for Clinical Trials document published by the U.S. Food and Drug Administration (FDA) under the reference FDA-1997-D-0508. These guidelines ensure that the statistical methods employed adhere to established clinical trial data analysis standards, ensuring rigor, reproducibility, and validity of findings.

Variables and tables will be presented in the order in which the sections are shown in the eCRF. Parameters recorded in more than one SI unit (e.g., lab units) will be converted into a single SI unit as appropriate.

Description of patients' characteristics

Prior to the analysis of the primary and secondary endpoints, the treatment groups (or any groups in subgroup analyses) will be compared about the following patients' characteristics:

- Demographics: age, sex, body weight, body mass index (BMI), obesity, and cigarette smoking.
- Characteristics of AMI at admission: type of acute myocardial infarction (STE- or NSTEMI), mechanical ventilation upon admission.
- Time delay: from symptoms to hospital, from symptoms to reperfusion.
- Out-of-hospital cardiac arrest: cardiopulmonary resuscitation before admission, first documented rhythm, time to return of spontaneous circulation (ROSC) (min), external cardiac massage - before admission, on admission, overall duration, mechanical ventilation, regulation of body temperature, target value.
- Patient's status at the time of admission: blood pressure - left arm systolic/diastolic (mmHg), blood pressure - right arm systolic/diastolic (mmHg), pulse rate (BPM), cyanosis, mydriasis, transient mydriasis, deep unconsciousness without prior treatment with hypnotics.
- Treatment with vasopressors and/or inotropic agents, noradrenaline, adrenaline, dopamine, dobutamine, another vasopressor agent, another inotropic agent.
- Analgosedation: analgosedation, opioid (morphine, fentanyl, sufentanil), benzodiazepine (midazolam, diazepam, other), propofol, another analgosedation method.

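### Does the non-inferiority decision lack a matching confidence interval, and is its 1% margin left undefined?

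*SAP*

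**What the plan says.** Under Primary endpoint – clinical, the SAP tests non-inferiority first and superiority only if non-inferiority is met. The Statistical analysis section gives the methods:

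- Non-inferiority: "The non-inferiority scenario will be assessed using a one-sided Z-test with a non-inferiority margin of 1"%.
- Endpoint comparisons in general: "The chi-square test will be employed for categorical variables, including the primary and secondary study endpoints".
- Level: "A p-value of 0.05 will be adopted as the threshold for determining statistical significance across all analyses".
- Presentation: "Relative risks and 95% confidence intervals will be used to describe and visualize the results of endpoint analysis", with counts and percentages for each study group.

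The power analyses list a significance level of 0.05 for both scenarios without saying one- or two-sided. The non-inferiority setting reads "Endpoint difference 10 % with a noninferiority margin of 1"%, with rates of 50% and 40%, and concludes that with "the noninferiority margin of 1%, 506 patients are needed to test the noninferiority hypothesis". The superiority setting, 50% vs 38%, concludes that "a total of 536 patients is needed to test the null hypothesis of no difference between groups".

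**The concern.** Non-inferiority is the first decision on the primary clinical endpoint, so the reader should be able to see it in the reported effect. Two things seem to prevent that.

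First, a one-sided 0.05 test against an absolute margin is equivalent to checking whether the upper limit of a two-sided 90% interval for the risk difference lies below the margin. The SAP plans a different level (95%) and a different scale (relative risk). One percentage point equals a relative risk of 0.51/0.50 = 1.02 at a 50% control rate and 0.41/0.40 = 1.025 at 40%, so no fixed relative-risk limit stands for the margin. A report could declare non-inferiority beside an interval that seems to deny it.

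Second, the sample-size section uses the same unqualified 0.05 for both scenarios and calls the margin simply 1%. If the margin could be read as relative, or the level as one-sided 0.025, the decision itself would be open to choice after the data are seen.

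**Working it through.** **Inputs.** From the SAP: power 0.8, level 0.05, 1:1 allocation; 50% vs 40% with margin 1% (non-inferiority); 50% vs 38% (superiority). Normal quantiles: 1.645 (one-sided 0.05), 1.960 (one-sided 0.025, or two-sided 0.05), 0.842 (power 0.8).

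**1. The stated non-inferiority size.** With an absolute margin, the distance from the assumed difference to the margin is 0.10 + 0.01 = 0.11. The mean rate is 0.45, so the pooled variance term is 2 × 0.45 × 0.55 = 0.495. The unpooled term is 0.25 + 0.24 = 0.49.

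n per arm = (z_α√0.495 + 0.842√0.49)² / 0.11²

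- One-sided 0.05: 252.06, so 253 per arm and **506** in total, as stated. With unpooled variance throughout: 250.4, so 502.
- One-sided 0.025: 320.1, so 642 (unpooled 636).
- Relative margin of 1.01 on the log scale, one-sided 0.05: (0.5/0.5 + 0.6/0.4)(1.645 + 0.842)² / (ln 1.01 − ln 0.8)² = 284.5, so 570.

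Of these, only an absolute margin at one-sided 0.05 gives 506.

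**2. A second anchor.** The Sample size calculation section also records the 2018 calculation: 50%, difference 10%, margin 5%, 270 patients. Absolute margin, one-sided 0.05, unpooled: 0.49 × (1.645 + 0.842)² / 0.15² = 134.6, so 135 per arm and **270**. (Pooled gives 272.) A relative margin of 1.05 on the log scale gives 209.02, so 210 per arm and 420. The pooled or unpooled convention moves these totals by 2 to 4 patients and does not affect the reading.

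**3. The superiority size.** With 50% vs 38%, pooled rate 0.44 and difference 0.12, two-sided 0.05 gives 267.4, so 268 per arm and **536**, as stated. One-sided 0.05 gives 210.5, so 422. The same 0.05 is thus one-sided for non-inferiority and two-sided for superiority, which agrees with the tests named in the Statistical analysis section.

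**4. Where test and interval part company.** Take 268 per arm and 134 control events (50%). For x cangrelor events, d = x/268 − 0.5 and SE = √[(0.25 + p(1−p))/268] with p = x/268. Limits are d + 1.645 SE (90%) and d + 1.960 SE (95%).

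| Cangrelor events | d (points) | Upper 90% limit of d | Upper 95% limit of d | Relative risk | Upper 95% limit of RR | One-sided p vs +1 point |
|---|---|---|---|---|---|---|
| 114 | −7.46 | −0.40 | +0.96 | 0.851 | 1.022 | 0.024 |
| 115 | −7.09 | −0.02 | +1.33 | 0.858 | 1.030 | 0.030 |
| 116 | −6.72 | +0.36 | +1.71 | 0.866 | 1.038 | 0.036 |
| 117 | −6.34 | +0.73 | +2.09 | 0.873 | 1.047 | 0.044 |
| 118 | −5.97 | +1.11 | +2.47 | 0.881 | 1.055 | 0.053 |

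Non-inferiority is declared up to 117 events. At 115 to 117 the 95% risk-difference limit lies beyond +1 point while the matching 90% limit is inside it.

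**5. How often.** Exact binomial enumeration at 268 per arm gives the probability that non-inferiority is declared with the 95% risk-difference limit at or beyond +1 point: 4.9% at 38% vs 50%, 7.8% at 40% vs 50% (both SAP assumptions), and 9.6% at 45% vs 50% (my assumption).

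**6. Error rate.** At a true excess of 1 point (51% vs 50%), non-inferiority is declared with probability 4.9%, in line with the planned 5%.

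**The case for a change.** The strongest case for a change is this. A margin that decides a primary endpoint should not have to be worked back from a sample size, and an interval on the margin's own scale should be fixed in advance rather than chosen once results are known. The split results arise at the trial's own design rates. Scale alone can cause one: at 114 events the 95% risk-difference limit is inside the margin (+0.96), while the relative-risk limit of 1.022 is just above 1.02.

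Part of this stands. No risk-difference interval is planned, and showing one at the 90% level, with the 95% interval, beside the relative risk would be good reporting.

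The rest does not carry far. The Statistical analysis section says one-sided and sets 0.05. In the sample-size line the 10% for 50% vs 40% can only be an absolute difference, since the relative reduction is 20%, and the margin stands next to it in the same unit. The SAP never sets the relative-risk interval against the margin; the conflict appears only after a reader converts 1 point into a relative risk. An interval with an upper limit of 1.03 to 1.05 that includes 1 is also the ordinary picture when non-inferiority is met and superiority is not. The example at 114 events turns on a gap of 0.002, which disappears at two decimals.

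**Conclusion.** No change to the plan is called for. An analyst who follows the SAP runs a one-sided 0.05 Z-test of the risk difference against +1 percentage point; the two stated sizes, 506 and 270, confirm that reading. The test holds its planned error rate, and the planned 536 patients exceed the 506 that non-inferiority needs. The missing risk-difference interval is a presentation detail that analysts fill sensibly from the promised counts and percentages, and adding it would alter no decision, error rate, power or enrolment figure.

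The apparent mismatch is confined to three event counts when the control arm has 134 events of 268, with a probability of 4.9% to 7.8% under the SAP's design rates. These figures rest on Wald intervals and complete data at 268 per arm. The conclusion takes one-sided 0.05 as the sponsor's chosen level, which the SAP applies consistently.

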5. Women of childbearing potential should be protected from pregnancy throughout the study (relevant for long-term use of ticagrelor). Suitable methods of contraception, in this case, include hormonal contraceptives, barrier methods, or complete withdrawal – as long as it is consistent with the patient's lifestyle.

Exclusion criteria

1. Contraindications to antiplatelet therapy with ticagrelor/cangrelor:
 - Recent (< 6 months) major bleeding,
 - Recent (< 1 month) major surgery/injury,
 - History of intracranial hemorrhage,
 - History of Stroke/TIA,
 - Known ticagrelor/cangrelor intolerance,
 - Severe hepatic impairment,
 - Co-administration of potent CYP3A4 inhibitors (e.g., ketoconazole, clarithromycin, nefazodone, ritonavir, and atazanavir).

2. Administration of a loading dose of oral P2Y₁₂ inhibitor before admission (clopidogrel ≥ 300 mg, ticagrelor 180 mg, prasugrel 60 mg).
3. Need for concomitant chronic anticoagulant treatment due to atrial fibrillation, artificial valve, thromboembolic disease, etc.

Study endpoints

Primary endpoint – laboratory

- Comparison of the effect of parenteral cangrelor with the recommended crushed ticagrelor treatment on periprocedural ADP-activated platelet aggregation; the periprocedural rate of onset and the proportion of patients who achieve effective* P2Y₁₂ platelet receptor inhibition defined by a Platelet Reactivity Index (PRI) value at the end of percutaneous coronary intervention.

**Platelet Reactivity Index (PRI) less than 50% as measured by the vasodilator-stimulated phosphoprotein (VASP) phosphorylation flow cytometric assay*

Primary endpoint – clinical

- Comparison of the effect of parenteral cangrelor with the recommended crushed ticagrelor treatment on the incidence of major cardiovascular events 30 days after enrollment in the study. The primary clinical endpoint is a composite of all-cause death, myocardial infarction, or stroke* within 30 days, expressed as a proportion of patients with any of these events. The primary clinical endpoint is non-inferiority, and if this is met, then superiority will be tested.

**Ischemic stroke (intracranial hemorrhage assessed as a BARC 3c bleeding)*

Secondary endpoints

Key secondary efficacy endpoint

- Death, myocardial infarction, urgent revascularization of the infarct-related artery, stent thrombosis, or ischemic stroke within 30 days and one year after study enrollment expressed as a proportion of patients with any of these events.

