The dual approach of automated electronic validation through TrialDB and manual verification by a monitor and investigating team aims to uphold the highest data quality standards, ensuring that the data submitted for analysis are accurate and reliable, thereby enhancing the overall integrity of the study findings. The final validation of endpoints is provided by the endpoint adjudication committee and approved by its chairperson. Each endpoint is evaluated by two independent experts, with a third expert resolving any disagreements, ensuring robust and unbiased endpoint classification.

Statistical analysis

Statistical software and responsibilities

The data will be reviewed and statistically processed in the statistical analysis center: Institute of Biostatistics and Analyses, Faculty of Medicine, Masaryk University, Brno, [name], MS.c. Ph.D. The analysis will be computed using SPSS 27.0.1 (IBM Corporation, 2021).

Handling of missing values and outliers

Missing values are subject to validation procedures and will be communicated with study sites using lists of detected problems. If correction of missing values is not possible, no imputation of missing values will be performed. The presence of outliers will be evaluated using visual inspection of the continuous variable distribution; detected outliers will be removed from the statistical computations.

Interim analysis

No interim analysis is planned for this study; the decision can be justified as follows:

Reduction of Type I Error: Conducting interim analyses introduces the risk of inflating the Type I error rate. By avoiding interim analyses, the SAP maintains the integrity of the statistical significance threshold (e.g., a p-value of 0.05).

Pragmatic Feasibility: Given the acute nature of myocardial infarction with cardiogenic shock, the timeline for endpoint occurrences (30 days for primary endpoints) is relatively short, reducing the value of interim results for decision-making purposes.

Cost and Logistical Considerations: Implementing interim analyses would require additional resources, such as re-randomization schemes, database locks, and independent review committees, which are unjustified given the study's endpoints and anticipated outcomes timeline.

To mitigate risks associated with the absence of interim analysis:

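### Two primary endpoints are each tested at the full 0.05 with no rule linking them; if a win on either counts, the chance of a false primary claim is up to about 10%

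*SAP*

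**What the plan says.** Under Study endpoints the SAP lists two primaries, headed "Primary endpoint – laboratory" and "Primary endpoint – clinical". For the clinical endpoint it gives an internal order: "The primary clinical endpoint is non-inferiority, and if this is met, then superiority will be tested". It gives no order between the clinical and the laboratory endpoint.

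Under Sample size calculation, the laboratory, non-inferiority and superiority analyses each carry their own setting, "Statistical significance level 0.05", and their own sample size: 124, 506 and 536.

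The later Statistical analysis section assigns the chi-square test to the primary and secondary endpoints and a one-sided Z-test with a 1% margin to non-inferiority. It closes with the general rule: "A p-value of 0.05 will be adopted as the threshold for determining statistical significance across all analyses".

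**The concern.** A plan with two primaries needs to say what counts as a positive trial: either endpoint, both, or one before the other. Each choice has its own alpha rule. This SAP makes no choice, and its one stated rule gives the full 0.05 to each endpoint. As written, a significant result on either could be reported as a primary finding at 0.05, although the chance of at least one such false finding is higher. The choice could also be made after the results are known, when one primary has succeeded and the other has not.

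**Working it through.** **Inputs, all from the SAP.** Laboratory endpoint: 70% vs 90%, about 150 VASP measurements reachable. Non-inferiority: 50% vs 40%, margin 1%. Superiority: 50% vs 38%. Power 0.8, level 0.05 and 1:1 allocation throughout.

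**Step 1. Reproduce the SAP's sample sizes, to see how much alpha each test spends.** Per arm, n = [z_α·√(2p̄(1−p̄)) + z_0.8·√(p₁(1−p₁)+p₂(1−p₂))]² / d², where p̄ is the mean of the two rates and z_0.8 = 0.8416.

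- Laboratory, two-sided 0.05, d = 0.20: (1.960·√0.32 + 0.8416·√0.30)²/0.04 = 61.6, so 62 per arm and **124** in total (SAP: 124).
- Superiority, two-sided 0.05, d = 0.12: (1.960·√0.4928 + 0.8416·√0.4856)²/0.0144 = 267.4, so 268 per arm and **536** (SAP: 536).
- Non-inferiority, one-sided 0.05, d = 0.10 + 0.01 = 0.11: (1.645·√0.495 + 0.8416·√0.49)²/0.0121 = 252.1, so 253 per arm and **506** (SAP: 506). One-sided 0.025 would give 642.

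So the laboratory endpoint and each step of the clinical endpoint spend the full 0.05, and non-inferiority spends it one-sided. The step from non-inferiority to superiority is ordered and adds no inflation.

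**Step 2. Chance of at least one false primary claim when either endpoint counts and both nulls are true.**

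- Independent tests: 1 − 0.95 × 0.95 = **9.75%**.
- Any dependence: at most 0.05 + 0.05 = **10%**.
- Only claims favouring cangrelor (0.025 for the two-sided laboratory test, 0.05 for one-sided non-inferiority): 1 − 0.975 × 0.95 = **7.4%**.

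**Step 3. Does correlation between the endpoints help?** Only about 150 of about 536 patients give laboratory data, so the correlation of the two test statistics cannot exceed about √(150/536) = 0.53. With two-sided tests and a bivariate normal model, the 9.75% becomes 9.72% at correlation 0.1, 9.51% at 0.3 and 9.07% at 0.5. The figure therefore stays between about 9.0% and 9.75%.

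**Step 4. If both endpoints must succeed.** There is then no inflation, but joint power falls. Laboratory power with 75 per arm is 87.2%, and superiority power with 268 per arm is 80.1%. If independent, the joint power is 0.872 × 0.801 = **70%**.

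**The case against.** The strongest reply is that the SAP's opening hypothesis joins the platelet effect and the clinical effect with *and*. If both had to be shown, no error would be inflated. But that sentence states what the investigators expect. No section turns it into a decision rule, and each endpoint is sized alone for 80% power, which is not how a both-must-win trial is sized.

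Second, the two endpoints answer different questions, one pharmacodynamic in about 150 patients and one clinical in 550. Few readers would mistake a PRI result for fewer deaths, and whether the two form one family is partly a matter of judgement. This limits the harm and points towards the simplest repair, but the SAP labels both as primary.

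Third, the figure is conditional. If the laboratory effect is real, as the planning rates assume, only the clinical null can be falsely rejected, and the error is no more than that test's own level. This stands as a limit on the 9.75%, but error control has to hold without assuming the laboratory effect.

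Fourth, counting only favourable superiority claims gives 1 − 0.975² = 4.9%. That leaves out non-inferiority, which is the first primary clinical claim, and the matching one-sided level for a single test is 2.5%.

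**Conclusion.** The point holds as a gap in the decision rule: two primaries, full alpha on each, nothing linking them. The error is up to about 10% if a win on either counts (9.75% with independence, both nulls true and errors counted in either direction). It is about 7.4% for claims favouring cangrelor, part of which comes from the one-sided 0.05 level of the non-inferiority test.

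Three stronger readings are tempting, and the SAP does not support them.

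- A reader might infer that the SAP promises 5% across its endpoints and breaks that promise. The sentence concerned, "By avoiding interim analyses, the SAP maintains the integrity of the statistical significance threshold (e.g., a p-value of 0.05", stands under Interim analysis and gives a reason for not taking interim looks. It makes no claim about several endpoints.
- A reader might count a third primary test, because the laboratory endpoint mentions "the periprocedural rate of onset and the proportion of patients who achieve effective" P2Y₁₂ inhibition, and arrive at 1 − 0.95³ = 14.3%. The SAP gives no separate power analysis for rate of onset. Both quantities would also come from the same patients and measure the same platelet inhibition, so independence is not credible. Rate of onset is an unclear part of the endpoint definition, not a counted use of alpha.
- A reader might argue that the SAP breaches the E9 guideline it cites. The text of that guideline is not in the documents, so this cannot be checked from them.

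**What to change.** Before unblinding, state in the SAP that the clinical endpoint, tested for non-inferiority and then superiority, is the single confirmatory primary. Report PRI below 50% at the end of PCI as a pharmacodynamic endpoint with an estimate and confidence interval and no confirmatory claim. This is a change of wording only. It needs no extra patients and leaves clinical power as it is; the price is that the laboratory result loses confirmatory status.

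Alternatives, if the laboratory endpoint must stay confirmatory:

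- **Fixed sequence.** Each endpoint keeps 0.05 and no sample size changes, but a failure on the first blocks any claim on the second. With the laboratory test first, the chance of a clinical superiority claim is about 0.872 × 0.801 = 70% (150 laboratory and 536 clinical patients, independent).
- **Both must succeed.** State this and restate the joint power, about 70% on the same figures.

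Splitting alpha is less attractive. With 0.01 for the laboratory and 0.04 for the clinical endpoint, laboratory power falls from 87% to 69% at 150 patients (80% to 59% at 124), and non-inferiority power falls by about 3 points before any alpha is passed back. With 0.025 for each, superiority power falls to 71.3% at 536 patients, and 648 would be needed to restore it.
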